8.2.3. Electrocardiograms

- Triplicate 12-lead ECG will be obtained as outlined in the SoA ([Table 1](#)) using an ECG machine that automatically calculates the heart rate and measures of PR, QRS, QT, and QTcF intervals.
- ECGs should be obtained after the subject has been supine for at least 5 minutes.
- At each time point at which triplicate ECGs are required, 3 individual ECG tracings should be obtained as closely as possible in succession, but no more than 2 minutes apart. The full set of triplicates should be completed in less than 4 minutes.

8.2.4. Clinical Safety Laboratory Assessments

- See Appendix 2/Section [10.2](#) for the list of clinical laboratory tests to be performed and the SoA ([Table 1](#)) for the timing and frequency. All protocol-required laboratory assessments must be conducted in accordance with the laboratory manual and the SoA.

- The investigator must review the laboratory report, document this review, and record any clinically relevant changes occurring during the study in the AE section of the eCRF. The laboratory reports must be filed with the source documents.
- All laboratory tests with values considered clinically significantly abnormal during participation in the study or within 14 days after the last dose of study drug should be repeated until the values return to normal or baseline or are no longer considered clinically significant by the investigator or medical monitor.
 - If such values do not return to normal/baseline within a period of time judged reasonable by the investigator, the etiology should be identified and the sponsor notified.
 - If laboratory values from non-protocol-specified laboratory assessments performed at the institution's local laboratory require a change in subject management or are considered clinically significant by the investigator (eg, SAE or AE or dose modification), then the results must be recorded in the eCRF.

8.2.5. Bladder and Bowel Movement Diary

The BBMD will be completed in accordance with the instructions in the SoA ([Table 1](#)).

Subjects will enter BM-related information into a paper diary, the BBMD, on an event-driven basis (ie, following each BM). The BM-related information will include the day and time of BMs and a report of stool consistency for each BM using the BSFS ([8](#)); BSFS (1=Separate hard lumps like nuts [difficult to pass] to 7=Watery, no solid pieces [entirely liquid]).

Subjects will enter bladder information into the BBMD, which will include the following questions:

In the past 24 hours...

- Did you have to urinate more frequently than normal? (yes/no)
- How many times did you urinate? (0 to 2; 3 to 6; 7 to 10; or 10+ times)
- Did you feel the strong need to urinate with little or no warning? (yes/no)
- Did you have to get up to urinate during the night more frequently than usual? (yes/no)
- How many times did you have to get up at night to urinate? (0, 1, 2, 3+ times)
- Did you have pain or burning in your bladder or pelvic area? (yes/no)

8.3. Adverse Events and Serious Adverse Events

The definitions of AEs and SAEs can be found in Appendix 3/Section [10.3](#).

AEs will be reported by the subject (or, when appropriate, by a caregiver, surrogate, or the subject's legally authorized representative).

The investigator and any qualified designees are responsible for detecting, documenting, and recording events that meet the definition of an AE or SAE and remain responsible for following

up AEs that are serious, considered related to the study intervention or study procedures, or that caused the subject to discontinue study drug (see Section 7).

8.3.1. Time Period and Frequency for Collecting AE and SAE Information

All AEs and SAEs will be collected from the signing of the ICF until completion of study participation (ie, early termination or Follow-up Phone Call) at the timepoints specified in the SoA (Table 1).

Any medical condition that is present at the time that a randomized subject is screened and does not deteriorate (worsen in severity and/or frequency) should be recorded as Medical History and not as an AE. However, if the subject's condition deteriorates at any time during the study, it will be recorded as an AE. AEs characterized as intermittent require documentation of onset and duration of each episode. Pretreatment AEs will be collected and captured in the subject's source documentation from the time the subject signs the ICF until the subject receives study drug. Pretreatment AEs in randomized subjects will additionally be entered on the AE page of the subject's eCRF. Laboratory abnormalities, changes in vital signs, and physical examination findings should be considered AEs and reported on the AE page of the subject's eCRF only if the investigator considers them clinically significant and/or they necessitate intervention.

All SAEs will be recorded and reported to the sponsor or designee immediately and under no circumstance should this exceed 24 hours, as indicated in Appendix 3/Section 10.3. The investigator will submit any updated SAE data to the sponsor within 24 hours of it being available.

Investigators are not obligated to actively seek AEs or SAEs after the conclusion of study participation. However, if the investigator learns of any SAE, including a death, at any time after a subject has been discharged from the study, and he/she considers the event to be reasonably related to the study intervention or study participation, the investigator must promptly notify the sponsor.

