Stool collection ^p			Check-in to Pre: 0h			1 sample collected between Day 7 (postdose) and Day 8 (predischarge)		
Hemoccult testing ^q			X			X		
Follow-up phone call ^r								X

^a Subjects will be discharged on Day 8 unless they have physical examination findings or laboratory abnormalities that are considered by the investigator to be clinically meaningful. In the event that a subject discontinues from the study, an ET Visit will be performed prior to discharge from the CRU. Every effort should be made and documented to ensure that safety procedures scheduled for Discharge are performed at the ET visit.

AE=adverse event; BBMD=bladder and bowel movement diary; CRP=C-reactive protein; CRU=clinical research unit; ECG=electrocardiogram; ESR=erythrocyte sedimentation rate; ET=Early Termination; FSH=follicle-stimulating hormone; HCG: human chorionic gonadotropin; HIV=human immunodeficiency virus; PK=pharmacokinetic; Post=postdose; Pre=predose; SARS-CoV-2=severe acute respiratory syndrome coronavirus 2; UA=urinalysis

^b Height will only be measured at the Screening Visit. On Day 1 (predose) and Discharge (Day 8), subjects will be weighed in the morning upon awakening and before they ingest any water or food.

^c A complete physical examination will be conducted except on Days 1 through 7 when the physical examination will be symptom-directed and conducted prior to study drug administration.

^d Rectal examination at all timepoints should include a digital rectal examination and visual inspection of the perianal area for redness or irritation. If significant redness, rectal pain, fever, bleeding, or mucus is observed, anoscopy may be performed as part of the rectal examination.

^e Vital signs will include oral temperature, blood pressure, and pulse rate. In a semisupine position, blood pressure and pulse will be obtained at the 0.5-hour postdose timepoint on Days 1 and 7 (consistent with the position required following dosing). Blood pressure and pulse at the 2-, 4-, and 8-hour postdose timepoints on Days 1 and 7, as well as predose on Days 3 through 6, should be preceded by at least 5 minutes of rest for the subject in a quiet setting without distractions (eg, television, cell phones). When applicable, vital sign measurements will be obtained before blood draws.

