4.2. Scientific Rationale for Study Design

A randomized, double-blind, placebo-controlled study design was chosen to investigate the effects of IW-3300 administered once daily for 7 days as a low-volume enema. Subjects will be randomized within each cohort to ensure that the treatment groups are comparable and to minimize the potential for selection bias. The study will be double-blind to ensure that the subjects and CRU staff are unaware of the treatment assignment and to minimize the potential for bias in study assessments or AE reporting. Placebo was chosen as the control so that the rate of spontaneously occurring AEs can be determined and to reduce the potential for bias in the reporting of AEs.

To ensure a thorough assessment of safety, subjects will be confined to the CRU for the duration of the Clinic Period, from Check-in (Day -1) through until Discharge (Day 8), which will occur after completion of the assessments (at least 24 hours after administration of study drug) and at the investigator's discretion. CRU staff will contact subjects for the Follow-up Phone Call on Day 21 (+3), conducted 14 days after the last dose, for safety follow-up; at the discretion of the investigator, subjects may be requested to return to the CRU for their follow-up contact.

To evaluate any effects of IW-3300 on bowel and bladder function, subjects will complete the BM portion of the BBMD on 7 consecutive days during the Screening Period to establish a

baseline for bowel function without study drug. Similarly, subjects will provide answers to the bladder/urinary-symptom-related questions in the BBMD predose on Day 1, with a 24-hour recall, to establish a baseline without study drug.

Because this is the first multiple-dose study with IW-3300 in humans, cohorts will be enrolled sequentially, following a safety review of prior dosed cohort(s) by a Dose Escalation Committee (Section 6.6). In addition, stopping criteria have been established to ensure that dosing at the same or higher dose levels will stop should a safety signal be detected (Section 7.1.1). In this case, a lower dose of IW-3300 could be used.

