7. DISCONTINUATION OF STUDY INTERVENTION AND SUBJECT DISCONTINUATION/WITHDRAWAL

7.1. Discontinuation of Study Intervention

It may be necessary for a subject to permanently discontinue study drug. A subject will be discontinued from study drug in the event of:

- A confirmed pregnancy
- A SAE considered by the investigator or Sponsor to be related to study drug

Dosing of study drug for an individual subject may be suspended temporarily as detailed in Section 7.1.1; if the subject is unable to resume dosing, they should follow the instructions for permanent discontinuation below.

If study drug is permanently discontinued, then the subject will have the safety evaluations scheduled for Discharge (Day 8) performed. See the SoA ([Table 1](#)) for data to be collected at the time of discontinuation and follow-up, and for any further evaluations that need to be completed.

If a subject is discontinuing study drug due to an AE, the AE must be followed until it is resolved, stable, or judged by the investigator to be not clinically significant.

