7.2. Subject Discontinuation/Withdrawal from the Study

- A subject may withdraw from the study at any time at his/her own request or may be withdrawn at any time at the discretion of the investigator for safety, behavioral, compliance, or administrative reasons. This is expected to be uncommon.
- At the time of discontinuation from the study, if possible, an ET visit should be conducted, as shown in the SoA ([Table 1](#)). See the SoA for data to be collected at the time of study discontinuation and follow-up and for any further evaluations that need to be completed.
- The subject will be permanently discontinued both from the study intervention and from the study at that time.
- If the subject withdraws consent for disclosure of future information, the sponsor may retain and continue to use any data collected before such a withdrawal of consent.
- If a subject withdraws from the study, he/she may request destruction of any samples taken and not tested, and the investigator must document this in the site study records.

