7.1. Adverse Events

AEs will be coded by SOC and PT using MedDRA Version 24.0. The study investigator will assess the severity of the AE and assign a grade using the Common Terminology Criteria for Adverse Events (CTCAE). An AE is considered a treatment-emergent AE (TEAE) if the AE started after initial study drug administration and within 1 day of the last dose of study drug. In addition, an AE that started before initial study drug but worsened after the first dosing of the study drug is also considered a TEAE.

The number and percentage of subjects reporting TEAEs in each treatment group (or cohort) will be tabulated:

- by SOC and PT
- by SOC, PT, and CTCAE grade
- by SOC, PT, and relationship to study drug.

If a subject has more than 1 TEAE coded to the same PT, the subject will be counted only once for that PT by identifying the TEAE with the highest CTCAE grade and the closest relationship to study drug.

The incidence of the following TEAEs will be summarized by PT:

- Treatment-emergent Serious Adverse Events (TESAEs)

All AE summary tables will be sorted alphabetically by SOC and each PT within the SOC will be sorted by decreasing frequency for the IW-3300 group.

A TEAE summary table with all the non-SAEs by SOC and PT will be generated to support the clinicaltrials.gov reporting requirements.

AE listings will be presented for all subjects with AEs, all screened subjects with SAEs, all SAEs (regardless of treatment-emergent status), and subjects who died (if any), respectively.

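### AE/SAE collection closes at early termination for subjects who leave the study, so new events after exit, including some inside the 1-day TEAE window, may go unsought

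*Protocol*

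**What the plan says.** **End of collection.** Protocol Section 8.3.1 runs AE and SAE collection from consent "until completion of study participation (ie, early termination or Follow-up Phone Call". After that, "Investigators are not obligated to actively seek AEs or SAEs after the conclusion of study participation". An SAE that the investigator later learns of and judges reasonably related must still be reported.

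**Leaving the study.** Section 7.2 covers withdrawal at the subject's own request or at the investigator's discretion, with safety among the grounds, and expects it to be uncommon. It states: "The subject will be permanently discontinued both from the study intervention and from the study at that time". It also points onward: "See the SoA for data to be collected at the time of study discontinuation and follow-up". Footnote a of the Schedule of Activities (SoA) says that "an ET Visit will be performed prior to discharge from the CRU" and gives no minimum interval after the last dose.

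**Stopping study drug only.** Section 7.1 says: "If study drug is permanently discontinued, then the subject will have the safety evaluations scheduled for Discharge (Day 8) performed". Nothing there removes the subject from the study.

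**Intended follow-up.** Section 4.2 describes the Day 21 (+3) call as "conducted 14 days after the last dose, for safety follow-up". Sections 4.1 and 4.1.1.2 describe a stay in the clinical research unit (CRU) of at least 24 hours after the last dose.

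**What is counted.** SAP Section 7.1 treats an AE as treatment-emergent if it starts after the first dose and "within 1 day of the last dose of study drug". Protocol Section 9.4.2 summarizes TEAEs for one calendar day after the last dose. Protocol Section 10.3.1.2 sets no upper limit.

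**The concern.** The primary endpoints are the incidences of TEAEs and TESAEs, in the first multiple-dose study of this drug. The rule in Section 8.3.1 makes the length of active AE collection depend on whether the subject stays. A completer is observed to the 14-day contact. A subject who leaves is observed only to the ET visit, and the text allows that visit before the 1-day TEAE window has closed.

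Safety is a named ground for withdrawal, so those with shortened observation may include subjects who tolerated treatment poorly. A new symptom that begins after such a subject goes home would meet the SAP's TEAE definition if it started within the window, but nobody is asked to look for it. Later events would meet the protocol's open-ended definition and belong in the AE and SAE listings, and they too would go unsought.

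**Working it through.** **1. Reproduce the plan's figure.** Last planned dose Day 7, call on Day 21 (+3):
- Day 21 − Day 7 = 14 days, as Section 4.2 states. With the +3 window, Day 24 − Day 7 = 17 days.
- Check on day numbering (no Day 0): 8 + 21 = 29 and 36 + 21 = 57, matching the stated total participation of 29 to 57 days.

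**2. Who is affected.** Section 7.1 (drug stopped) requires the Day 8 evaluations and refers to the SoA for follow-up. Section 7.2 (study left) ends drug and study together. SAP Section 6.1 counts the two dispositions separately. Only the Section 7.2 group meets the early-termination limb of Section 8.3.1.

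**3. Uncollected part of the TEAE window.** Let h be the hours from last dose to ET. The documents give no value, so 2 to 24 hours is assumed.
- SAP window read as 24 hours: uncollected = max(0, 24 − h).
- One calendar day (Section 9.4.2) read as running to the end of the next day, with a 09:00 dose assumed: window = 15 + 24 = 39 hours; uncollected = max(0, 39 − h).

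| ET at h hours | 24-hour window | Calendar-day window |
|---|---|---|
| 2 | 22 h | 37 h |
| 4 | 20 h | 35 h |
| 8 | 16 h | 31 h |
| 12 | 12 h | 27 h |
| 24 | 0 h | 15 h |

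If the 24-hour stay applies to ET subjects, the first reading has no gap; the second still does.

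**4. How much of the follow-up shortfall reaches the TEAE tables.** The shortfall against a completer is 14 × 24 − h = 336 − h hours. The share inside a 24-hour window is (24 − h)/(336 − h):
- h = 2: 22/334 = 6.6%
- h = 12: 12/324 = 3.7%

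The rest cannot change the SAP's TEAE tables for events that start after the last dose. It can change the listings, because SAP Section 7.1 lists all subjects with AEs, and SAEs regardless of treatment-emergent status.

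**5. Weight of one subject.** Each dose level has 6 active subjects, so one missed event moves a preferred-term row by 1/6 = 16.7 percentage points. Overall TEAE incidence counts subjects. If the one who left already has a TEAE, the change there is 0.

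**6. After the fix.** A contact at least 14 days after the last dose makes the uncollected part 0 hours under either reading. Keeping the Day 21 call is enough when the last dose is on or before Day 7: Day 7 gives 14 days, and Day 3 gives 21 − 3 = 18.

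**The case against.** **The 24-hour stay may already cover this.** Section 4.1 keeps subjects in the CRU for at least 24 hours after the last dose, and Section 6.7 and SoA footnote a allow discharge to be delayed for safety findings, so symptomatic subjects are the likeliest to be kept. This stands in part. An exit within hours is possible under the text but not prescribed by it. However, Section 7.2 lets a subject leave at any time, and nothing says that the stay binds someone who does.

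**The SoA may already keep the call.** Section 7.2 refers to the SoA for follow-up, and the SoA has AE monitoring in its Follow-up column with no exemption after ET. That reading is available, but it conflicts with Section 8.3.1, which names early termination as an end of collection. Sites could act either way.

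**Known events are not lost.** This stands. Sections 6.7, 7.1 and 8.3.3 follow ongoing AEs, including the one that led to stopping. Only new-onset events are at issue.

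**The primary tables barely move.** This largely stands, as the last two calculations above show. No hypothesis testing is planned, and withdrawal is expected to be uncommon.

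**Conclusion.** The point holds for subjects who leave the study under Section 7.2. For them the stated rule ends collection of new AEs at an ET visit with no minimum time after dosing, and the 14-day contact is not clearly retained. Between 12 and 22 hours of a 24-hour TEAE window is unobserved if exit falls 2 to 12 hours after dosing and the 24-hour stay does not apply. The gap is zero if the stay does apply and the window is 24 hours. The main effect is on AE/SAE listings, individual preferred-term counts and the open-ended definition in Section 10.3.1.2.

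Three stronger readings are tempting but not supported:
- **Anyone who stops dosing for intolerance loses follow-up.** Stopping study drug under Section 7.1 is not early termination.
- **Overall TEAE incidence is understated by 17 points, in the drug's favor.** A subject leaving for intolerance will usually already be counted. The 1/6 figure applies to a single preferred-term row, or to a subject with no earlier TEAE. An effect on overall incidence is possible but probably small.
- **The Day 21 call can fall less than 14 days after the last dose when dosing is suspended and resumed.** Section 6.1.1 fixes dosing to Days 1 through 7, and no text provides for doses after Day 7.

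**What to change.** In Protocol Sections 8.3.1 and 7.2 and SoA footnote a, replace the early-termination endpoint with one rule. New AEs and SAEs are collected for every dosed subject, including early terminators unless they withdraw consent to contact, until a follow-up phone contact at least 14 days after that subject's last dose. Keeping the scheduled Day 21 call meets this when the last dose is on or before Day 7. Make the same change in the SoA copied into SAP Section 11.3.

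Two clarifications belong with it. State whether the 24-hour stay described in Section 4.1 is meant to apply to early terminators. Reconcile the three TEAE limits (SAP Section 7.1, Protocol Sections 9.4.2 and 10.3.1.2), so that it is clear which later events enter the tables and which only the listings.

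The cost is a wording amendment and one extra phone call per early terminator, made by CRU staff who already make these calls.

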8.3.2. Method of Detecting AEs and SAEs

The method of recording, evaluating, and assessing causality of AEs and SAEs, and the procedures for completing and transmitting SAE reports are provided in Appendix 3/Section 10.3.

Care will be taken not to introduce bias when detecting AEs and/or SAEs. Open-ended and nonleading verbal questioning of the subject is the preferred method to inquire about AE occurrences.

8.3.3. Follow-up of AEs and SAEs

After the initial AE/SAE report, the investigator is required to proactively follow each subject at subsequent visits/contacts. Subjects with ongoing AEs or other safety concerns will be followed until resolution or until no further queries or follow-up actions are required. All SAEs will be followed until resolution, stabilization, the event is otherwise explained, or the subject is lost to follow-up (as defined in Section 7.3). Further information on follow-up procedures is provided in Appendix 3/Section 10.3.3.

8.3.4. Regulatory Reporting Requirements for SAEs

- Prompt notification by the investigator to the sponsor of an SAE is essential so that legal obligations and ethical responsibilities towards the safety of subjects and the safety of a study intervention under clinical investigation are met.
- The sponsor has a legal responsibility to notify both the local regulatory authority and other regulatory agencies about the safety of a study intervention under clinical investigation. The sponsor will comply with country-specific regulatory requirements relating to safety reporting to the regulatory authority, institutional review boards (IRBs)/independent ethics committees (IECs), and investigators.
- For all studies except those utilizing medical devices, investigator safety reports must be prepared for suspected unexpected serious adverse reactions (SUSARs) according to local regulatory requirements and sponsor policy and forwarded to investigators as necessary.
- An investigator who receives an investigator safety report describing an SAE or other specific safety information (eg, summary or listing of SAEs) from the sponsor will review and then file it along with the IB and will notify the IRB/IEC, if appropriate according to local requirements.

